Study Day within Period	≤ 28 days pre-dose ^b			Day 1 (hour post dose)				D2	D3	D5	D8	D12 ^w (± 1 D)	D15 ^w (± 2 D)	D22 ^w (± 2 D)	D29 (± 3 D)	D60 ^w (± 5 D)	D90 ^w (± 5 D)	D120 (± 7 D)	D150 Post-trial ^{c,w} (± 7 D)	D164 Phone Call (± 7 D)	
Scheduled Hour	Scn 1	Scn 2	Scn3 ^b	Pre-dose	0	1	3.5	8	12	24	48	52	96	168							
AE/SAE review ^m	X-----X																				
Serum β -Human Chorionic Gonadotropin (β -hCG)	X			X															X	Female participants only	
Serum Follicle Stimulating Hormone (FSH)	X																			Post-meno-pausal/oophorectomized female participants only	
Laboratory Procedures/Assessments																					
HIV/hepatitis screen	X																			Per site SOP	
Serum/saliva Drug and Alcohol Breath test ⁿ	X		X	X																Per site SOP	
Hematology, Chemistry, ^o	X		X	X				X	X			X	X	X	X	X	X	X	X		
aPTT and PT at Local Lab	X				X ^p		X	X		X	X ^y	X	X	X	X		X				
Hemoccult Test ^q		X						X		X	X	X	X	X	X	X	X				
Blood for Genetic Analysis ^r				X																	
Pharmacokinetics Evaluations																					
Blood for Plasma MK-2060 ^{s,x}				X	X ^t		X	X	X	X	X	XX	X	X	X	XX	X	X	XX		

Study	Panels ^a A, B, and C																			Notes	
	≤28 days pre-dose ^b			Day 1 (hour post dose)				D2	D3	D5	D8	D12 ^w (±1D)	D15 ^w (±2D)	D22 ^w (±2 D)	D29	D60 ^w (±5 D)	D90 ^w (±5 D)	D120 (±7 D)	D150 Post-trial ^{c,w} (±7 D)	D164 Phone Call (±7 D)	
Scheduled Hour	Scn 1	Scn 2	Scn3 ^b	Pre-dose	0	1	3.5	8	12	24	48	52	96	168							
Pharmacodynamic Evaluations																					
Blood for PT/aPTT/ FXI Activity by Central Lab ^x				X		X ^t		X	X	X	X	X	XX	X	X	X	XX	X	X		
Blood for Fibrin Generation Assay ^x				X		X ^t		X	X	X	X	X	XX	X	X	X	XX	X	X	X	
Blood for biomarker(s) of inflammation (e.g., hsCRP) Assay ^{t,x}				X		X ^t		X	X	X	X	X	XX	X	X	X	XX	X	X		
Blood for plasma ADA				X											X	X	X	X	X	X	
5-D Pruritus Scale (Panel C only)																		X			

- Participants may only participate in 1 Panel.
- Screening 3 should occur within 80 hours prior to Day 1.

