
1.3.2 Part 2

Study Period	Screening ≤28 days to Day 1		Intervention																Post- study	Notes	
	Scnl	Scn ^{2d}	Week 1				Week 2		Week 3		Week 4				Post Week 4						
			1	2	3	5	8	10	15	17	22	23	24	26	29	35	42	49	63	81	111
Visit Window (Day)			NA	NA	NA	NA	NA	NA	±1	NA	±1	NA	NA	NA	+1	NA	±2	±2	±2	±3	±3
Administrative Procedures																					
Informed Consent	X																				Sec. 8.1.1, 8.9 and 10.6 (Appendix 6)
Informed Consent for Future Biomedical Research	X																				
Inclusion/Exclusion Criteria	X	X	X																		Sec. 5.1, 5.2 and 8.1.2, Day 1 at predose
Participant Identification Card		X																			Sec. 8.1.3
Participant Bracelet			X																		Sec. 4.3.5
Assignment of Screening Number	X																				Sec. 8.1.6
Assignment of Allocation Number			X																		See Section 8.1.7, at Day 1 predose
Clinic Procedures																					
Medical History	X																				Sec. 8.1.4
Prior/Concomitant Medications Review		X-----																X			Sec. 6.5 and 8.1.5
MK-2060 or Placebo Administration			X	X		X	X	X		X		X									Sec. 8.1.8 and 8.6
On site Hemodialysis		X	X		X	X	X		X		X							X			See footnote b
Meals			X					X		X		X									Sec. 5.3.1
Domiciling			X	X	X	X	X	X		X		X									Sec. 8.1.11
Safety Procedures																					
Physical Examinations	X		X	X	X		X	X	X	X	X	X	X	X		X	X	X	X	X	Sec. 8.3.1, include a local IV infusion reaction assessment at all postdose PE
Systemic Infusion Reaction Assessment			X	X	X	X	X	X	X	X	X	X	X	X							Sec. 8.4.1
Assessment of Time to Hemostasis		X	X		X	X	X		X		X						X				Sec. 8.3.4. ~4 hrs postdose on each dosing days
Height	X	X																			Sec. 8.3.1

Study Period	Screening ≤28 days to Day 1	Intervention																	Post- study	Notes		
		Week 1		Week 2		Week 3		Week 4		Post Week 4					111							
Scheduled Week/Day	Scn1	Scn2 ^d	1	2	3	5	8	10	15	17	22	23	24	26	29	35	42	49	63	81	Sec. 8.11 for Visit Requirements and Sec. 8.11.6 for Timing of Procedure	
			NA	NA	NA	NA	NA	NA	±1	NA	±1	NA	NA	NA	+1	NA	±2	±2	±3	±3		±7
Visit Window (Day)																					X	
Weight	X	X																				
Resting Vital Signs (blood pressure, heart rate, respiratory rate, body temperature)	X	X	X	X	X	X	X	X	X	X	X	X	X	X			X	X	X		Sec. 8.3.2 Predose, 15 min, 30 min, and 1, 2, 3.5 and 12 hrs postdose on each dosing days	
Orthostatic Vital Signs (blood pressure, heart rate)	X	X	X	X	X	X	X	X	X	X	X	X	X								Sec. 8.3.2. Predose and 12 hrs postdose on each dosing days	

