12-lead electrocardiogram	X		X	X	X	X	X	X	X	X	X	X	X		X					X	Sec. 8.3.3. Predose and 3.5 hrs postdose on each dosing days	
Laboratory Procedures/Assessments																						
Safety Lab	Hematology and Chemistry	X	X	X		X		X	X	X	X	X	X		X		X	X	X	X	Sec. 8.4.3, 10.2 (Appendix 2) and 10.9 (Appendix 9).	
	aPTT/PT at Local Lab	X		X(3)		X(2)	X(2)	X(2)	X	X(2)	X	X(2)	X	X	X	X	X	X	X	X	Day 1: Predose, 1 and 12 hrs postdose. Predose may be performed within 3 days of dosing. Days 3, 5, 8, 15 and 22: 1 and 12 hrs postdose.	
	Hemoccult Test		X		X		X	X	X	X	X	X	X		X	X	X	X	X	X	Sec. 8.4.3, 8.11.6, 10.2 (Appendix 2) and 10.9 (Appendix 9).	
	HIV/hepatitis Screen	X																			Per site SOP	
	Serum/saliva Drug and Alcohol Breath Test	X	X	X																	Per site SOP	
	Serum Follicle Stimulating Hormone (FSH)	X																			Postmeno-pausal/oophorectomized female participants only	
	Serum β-Human Chorionic Gonadotropin (β-hCG)	X																		X	Female participants only	
	AE/SAE review	X																		X	Sec. 8.5 and 10.3 (Appendix 3)	

Study Period	Screening ≤28 days to Day 1	Intervention																		Post- study	Notes		
		Week 1		Week 2		Week 3		Week 4		Post Week 4													
Scheduled Week/Day	Scn1	Scn2 ^d	1	2	3	5	8	10	15	17	22	23	24	26	29	35	42	49	63	81	111	Sec. 8.11 for Visit Requirements and Sec. 8.11.6 for Timing of Procedure	
			NA	NA	NA	NA	NA	±1	NA	±1	NA	NA	NA	+1	NA	±2	±2	±2	±3	±3			
Pharmacokinetics																							
Blood for Plasma MK-2060 Assay			X(3)	X	X(2)	X(2)	X(2)	X	X(2)	X	X(3)	X	X	X	X	X	X	X	X	X	Sec. 8.7 Days 1 & 22: predose, 1h (within 5 min end of infusion), 12h. Days 3, 5, 8 & 15: predose, 1h (end of infusion). See footnote e, f.		
Pharmacodynamics																							
Blood for PT/aPTT/ FXI Activity by Central Lab			X(2)	X	X	X	X	X	X	X(2)	X	X	X	X	X	X	X	X	X	X	Sec. 8.8, Days 1 and 22 (2 draws): predose and 1h (within 5 min end of infusion).		
Blood for Fibrin Generation Assay			X(2)	X	X	X	X	X	X	X(2)	X	X	X	X	X	X	X	X	X	X			
Blood for biomarker(s) of inflammation (e.g., hsCRP) Assay			X				X		X		X				X	X	X	X	X	X			
Biomarkers																							
Blood for plasma anti-drug antibody			X							X		X						X	X	X	X	See Section 8.9 On dosing Days 1, 15, and 22: draw sample at predose.	
Blood for Genetic Analysis			X																			See footnote c.	
5-D Pruritus Scale												X				X							

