5.1 Inclusion Criteria

A participant will be eligible for inclusion in the study if the participant:

Type of Participant and Disease Characteristics

1. ESRD maintained on stable outpatient HD regimen, using an established (>3 months) and normally functioning, regular flow, uninjected mature AV fistula or AV graft and skin consistent with standard chronic HD access injuries, and HD stability defined as $Kt/V \geq 1.2$ within 3 months prior to dosing at a healthcare center for > 3 month from dosing.
2. On HD regimen at least 3 times per week for a minimum of 3 hours per dialysis session, using a complication-free well-maintained AV fistula or AV graft, expected and plan to continue this throughout and for at least 3 months beyond the study.
3. Have a Body Mass Index (BMI) ≥ 18 and $\leq 45 \text{ kg/m}^2$. BMI = weight (kg)/height (m) 2 .
4. Baseline health is judged to be stable based on medical history, physical examination, vital sign measurements and ECG performed prior to randomization.

5. Liver function test (serum alanine aminotransferase [ALT] and aspartate aminotransferase [AST]) must be equal to or below 1.5X upper limit of normal (ULN) and deemed not clinically significant by both the investigator and the Sponsor.
6. Be willing to comply with the trial restrictions (see Section 5.3) for a complete summary of trial restrictions).

Demographics

7. Be male or female, of non-child bearing potential (WONCBP) from 40 years to 80 years of age inclusive for Part 1, and 18 years to 80 years of age inclusive for Part 2, at the time of signing the informed consent.

Male Participants

Contraceptive use by men should be consistent with local regulations regarding the methods of contraception for those participating in clinical studies.

8. Agree to use a male condom plus partner use of an additional contraceptive method when having penile-vaginal intercourse with a WOCBP who is not currently pregnant. Note: Men with a pregnant or breastfeeding partner must agree to remain abstinent from penile-vaginal intercourse or use a male condom during each episode of penile-vaginal penetration.

Female Participants

Contraceptive use by women should be consistent with local regulations regarding the methods of contraception for those participating in clinical studies.

9. A female participant is eligible to participate if she is not pregnant or breastfeeding, and one of the following conditions applies:

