 - a. She is not a woman of childbearing potential (WOCBP), satisfying one of the two criteria below:
 - i. If the participant is a postmenopausal female: she is without menses for at least 1 year and has a follicle stimulating hormone (FSH) value in the postmenopausal range upon pre-study (screening) evaluation.
 - ii. If the participant is a surgically sterile female: she is status post hysterectomy, bilateral salpingectomy, oophorectomy or tubal ligation. NOTE: These procedures must be confirmed with medical records. In the absence of documentation, hysterectomy may be confirmed by pelvic exam or if necessary by ultrasound; oophorectomy may be confirmed by hormone levels, particularly follicle stimulating hormone (FSH) in the post-menopausal range, but tubal ligation without records

should be excluded. Information must be captured appropriately within the site's source documents.

Informed Consent

10. The participant (or legally acceptable representative) has provided documented informed consent/assent for the study. The participant may also provide consent/assent for FBR. However, the participant may participate in the study without participating in FBR.

Additional Categories

Consent must be documented by the participant's dated signature or by the participant's legally acceptable representative's dated signature on a consent form along with the dated signature of the person conducting the consent discussion.

A copy of the signed and dated consent form should be given to the participant before participation in the trial.

The initial informed consent form, any subsequent revised written informed consent form and any written information provided to the participant must receive the IRB/ERC's approval/favorable opinion in advance of use. The subject or his/her legally acceptable representative should be informed in a timely manner if new information becomes available that may be relevant to the participant's willingness to continue participation in the trial. The communication of this information will be provided and documented via a revised consent form or addendum to the original consent form that captures the subject's dated signature or by the participant's legally acceptable representative's dated signature.

Specifics about a trial and the trial population will be added to the consent form template at the protocol level.

The informed consent will adhere to IRB/IEC requirements, applicable laws and regulations and Sponsor requirements.

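### As extracted, the Part 2 schedule has no Day 1 pre-dose serum β-hCG test, unlike Part 1: a minor gap, cheap to close once the source table confirms it

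*Combined protocol and SAP*

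**What the plan says.** **Schedules.** Part 1 (Section 1.3.1) lists "Serum β -Human Chorionic Gonadotropin (β -hCG" with marks at Screening 1, Day 1 pre-dose and the post-trial visit. Part 2 (Section 1.3.2) lists "Serum β-Human Chorionic Gonadotropin (β-hCG" with marks, as extracted, at Screening 1 and poststudy only. The Part 2 screening header reads "Screening ≤28 days to Day 1". Screening 2, within 80 hours of Day 1 (Section 8.11.1), carries no β-hCG mark.

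**Eligibility.** Criterion 9 in Section 5.1 states: "A female participant is eligible to participate if she is not pregnant or breastfeeding". The Part 2 schedule has eligibility reviewed again on the day of first dosing; its note reads "Sec. 5.1, 5.2 and 8.1.2, Day 1 at predose". Only women of non-childbearing potential may enrol. Criterion 9 counts a woman as surgically sterile if "she is status post hysterectomy, bilateral salpingectomy, oophorectomy or tubal ligation", confirmed from medical records; tubal ligation without records is excluded. The age range in criterion 7 is "18 years to 80 years of age inclusive for Part 2", against 40 to 80 for Part 1. Part 2 gives six doses and Part 1 gives one (Table 2).

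**Other testing provisions.** Table 8 in Appendix 2 lists the pregnancy test as needed, and the appendix allows extra tests if the investigator finds them necessary. Appendix 5 (Section 10.5.2) calls for a test after a missed cycle or on suspicion of pregnancy.

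**Reason for the restriction.** Section 4.2 explains that women of childbearing potential are kept out because reproductive toxicology work in animals is unfinished.

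**The concern.** The two parts of one protocol treat the same check differently. The part with younger women and repeated dosing appears to have the weaker schedule, and no reason is given. The Day 1 re-check of non-pregnancy in Part 2 would then rest on a result that may be four weeks old.

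What is at stake is narrow. Postmenopausal or hysterectomized women gain nothing useful from a repeat test. A premenopausal woman with a documented tubal ligation might. A pregnancy that began after Screening 1 and had not yet led to a missed cycle would meet no scheduled test before the first infusion. Section 4.3.5 gives a half-life of about 18 days in this population, so withholding later doses would not end exposure promptly. A test before the first dose could prevent it.

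**Working it through.** The plan states no figure for the age of the pregnancy result, so there is nothing to reproduce. The check is a reading of the tables plus day counts.

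**1. Is the blank cell really Day 1?** The Part 2 header has 21 visits, but rows in the laboratory block have 19 data cells, so positions must be anchored.
- The local aPTT/PT row begins X, blank, X(3), blank, X(2), X(2), X(2), X, X(2), X, X(2). Its note gives "Day 1: Predose, 1 and 12 hrs postdose", which is three draws, and two draws on each of Days 3, 5, 8, 15 and 22. Against the header (Screening 1, Screening 2, Days 1, 2, 3, 5, 8, 10, 15, 17, 22) all eleven cells fit. The third cell is therefore Day 1, and the two missing cells in that row fall after Day 22.
- The hematology/chemistry row has 15 marks. Appendix 8 counts 2 pre-study + 12 treatment + 1 post-trial = 15 collections. Its first three cells are all marked: two screening visits, then Day 1.
- The drug and alcohol row is marked in the same three cells.
- The β-hCG row is marked in the first cell and blank in the second and third.

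**2. Does other text fill the gap?** Table 8 and Appendix 2 permit a Day 1 test without requiring one. Appendix 5 is event-driven. The Day 1 eligibility review names no test.

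**3. Age of the last scheduled result at first dosing.**
- Part 2 as extracted: the maximum equals the screening window, 28 days.
- With a Day 1 pre-dose test inside the 24-hour window for pre-dose safety labs (Section 8.11.6): 24 h ÷ 24 h per day = 1 day at most.

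**4. Number of extra assays.** Section 6.3.2 requires at least 3 participants of each gender in Part 2. Taking the approximate total as exactly 20, without replacements, the range is 3 women to 20 − 3 = 17 women.

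**5. Blood volume (Appendix 8).** Safety labs in Part 1: 12 × 12.5 = 150 mL. In Part 2: 15 × 12.5 = 187.5 mL. The volume per collection is the same, and neither part has a β-hCG line, although Part 1 schedules three such tests. If β-hCG is run on the safety-lab sample, no extra blood is needed.

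**The case against.** **The table is unreliable.** This is the strongest objection. The AE/SAE row directly below shows the same pattern, one mark at each end, yet Section 8.5.1 requires continuous reporting. The dosing row shows seven marks for six doses, some under the wrong days. The aPTT/PT row adds up to 24 draws, against 25 in Appendix 8. Knowing where a mark would sit does not prove that none was there. Part of this stands: a lost mark cannot be excluded. But the AE/SAE row more plausibly lost a connecting line, as Part 1 prints one there, than a discrete mark. The nearby hematology/chemistry row reconciles exactly, and the aPTT/PT row fits the header through Day 22.

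**Eligibility already controls the hazard.** This stands, and it sets the weight of the point. Postmenopausal status needs a year without menses plus FSH in range, and surgical sterility needs records. Appendix 5's list of women of non-childbearing potential omits tubal ligation, which criterion 9 accepts. On the appendix's definition, the group most helped by the test would not qualify. That conflict is a separate matter, but it is one more reason the group may be empty.

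**Stronger readings the documents do not support.**
- A reader might infer that women able to conceive will be dosed untested. The protocol excludes them, and every woman is tested at Screening 1.
- The range of 3 to 17 might be taken as women at risk. It counts added assays; the number with tubal ligation is not given.
- A reader might extend the point to doses 2 to 6. The event-driven rule in Appendix 5 covers that period, and single-dose Part 1 offers no benchmark for it.
- The lower age limit in Part 2 might suggest a check dropped by oversight. Nothing in the protocol shows why the schedules differ.

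**Conclusion.** The point holds as a minor improvement, subject to confirming the cell in the source table. As extracted, Part 2 lacks the Day 1 pre-dose β-hCG that Part 1 has, and no other provision requires one. The last scheduled result can be up to 28 days old at first dosing, against at most 1 day with the added test. These figures are worst-case ages of a result, not risks of pregnancy. Absolute risk is very low, and the women for whom the test would matter may number zero. No safety, PK or PD analysis depends on it. The conclusion assumes that the third data cell of the β-hCG row is Day 1, that no mark was lost there in extraction, and that Screening 1 may use the full window.

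**What to change.** Check the Part 2 β-hCG row in the source document. If Day 1 is marked there, nothing needs to change. If it is blank, add a Day 1 pre-dose mark for female participants, as in Part 1, and run the assay on the safety-lab blood taken within 24 hours before dosing. Participants are admitted the evening before (Section 8.1.11), so the sample can be drawn at admission. Section 8.11.2 places randomization after all pre-dose procedures, so the result can be required by then.

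The cost is one schedule cell and one assay per woman, about 3 to 17 in total, probably with no extra blood if the safety-lab sample is used. The main burden is turnaround: the result must be back before randomization.

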2 INTRODUCTION

2.1 Study Rationale

MK-2060 is an anti-FXI monoclonal antibody being developed for the prevention of thrombotic complications in end-stage renal disease (ESRD). The purpose of this study is to assess the safety, tolerability, PK, and PD of MK-2060 after IV administration of single and multiple doses in older adult participants with ESRD on HD. Data from this trial will be used to aid dose selection of MK-2060 in future trials.

2.2 Background

Refer to the IB for detailed background information on MK-2060.

2.2.1 Pharmaceutical and Therapeutic Background

FXI is a critical component in the intrinsic pathway of the coagulation cascade. MK-2060 is an anti-FXI monoclonal antibody being developed for the prevention of thrombotic complications in ESRD. Based on preclinical and human genetic data, as well as emerging clinical data using an anti-sense oligo (ASO) approach [Buller, H. R., et al 2015] [Bethune, C., et al 2017]. FXI inhibition is predicted to confer a clinically relevant antithrombotic effect with a reduced risk of bleeding complications and hence an expanded therapeutic index compared to inhibition of more downstream clotting factors such as FXa and thrombin. Therefore, FXI/FXIIa inhibition is a promising therapeutic approach for the prevention of thromboembolic complications.

2.2.2 Ongoing Clinical Studies

Protocol 001

Protocol MK-2060-001 is a double-blind, randomized, placebo-controlled, single site, sequential panel study to evaluate the safety, tolerability, PK, and PD of single ascending dose administration of SC and IV doses of MK-2060 in healthy male participants. The clinical conduct of PN001 is complete. 36 healthy male participants received single SC doses of MK-2060 up to 120 mg and 24 healthy male subjects received single IV doses of MK-2060 up to 40 mg. MK-2060 was generally well-tolerated and there were no SAEs or discontinuations due to AEs. Refer to the IB Edition 4 for a detailed overview of the study, and available preliminary PK, PD, and safety results.

Protocol 004 Part 1 Panels A, B and C:

As of 09-Oct-2020, 24 participants have been administered one IV dose up to 40 mg MK-2060 or placebo. To date, single IV doses up to 40 mg have been generally well tolerated and there have been no treatment emergent SAEs and no discontinuations due to any drug-related AEs. There have been no AEs suggestive of hypersensitivity. Refer to IB Edition 4 for a detailed overview of preliminary safety, PK and PD results for Part 1 Panels A, B and C.

2.3 Benefit/Risk Assessment

Participants in clinical trials generally cannot expect to receive direct benefit from treatment during participation, as clinical studies are designed to provide information about the safety and effectiveness of an investigational medicine.

Additional details regarding specific benefits and risks for participants participating in this clinical study may be found in the accompanying IB and informed consent documents.

3 HYPOTHESES, OBJECTIVES, AND ENDPOINTS

This study is to be conducted in adult participants with End-Stage Renal Disease on Hemodialysis.

Objectives	Endpoints
Primary	

Objective: Part 1: To evaluate the safety and tolerability of MK-2060 following single dose IV administration in older adult participants with ESRD on HD. Part 2: To evaluate the safety and tolerability of MK-2060 following multiple dose IV administration including an IV loading dose in older adult participants with ESRD on HD.	
AEs (including local infusion site reactions and systemic reactions to infusion), physical examinations, vital signs, 12-lead ECGs, laboratory safety tests (serum chemistry, hematology), aPTT, PT, and endpoints related to bleeding (macroscopic bleeding, high sensitivity hemoccult) will be assessed throughout the dosing intervals.
Secondary	
Part 1: MK-2060 plasma AUC_{0-∞}, AUC₀₋₁₆₈, C_{max}, C₁₆₈, T_{max}, terminal t_{1/2}, CL and V_dPart 2: MK-2060 plasma AUC₀₋₁₆₈, C_{max}, C₁₆₈ (C_{min}), T_{max}

Objectives	Endpoints

• Objective: Part 1: To evaluate the effect of MK-2060 on aPTT following single dose IV administration in older adult participants with ESRD on HD. Part 2: To evaluate the effect of MK-2060 on aPTT following multiple dose IV administration including an IV loading dose in older adult participants with ESRD on HD.• Hypothesis: Part 1: The true fold increase from baseline for aPTT 168 hours after a single well-tolerated dose of MK-2060 in older adult participants with ESRD on HD is at least 1.5. Part 2: The true fold increase from baseline for aPTT 168 hours post the last dose following an IV loading dose and three maintenance IV doses of MK-2060 in older adult participants with ESRD on HD is at least 1.5.	
• aPTT fold change from baseline

Part 1:
 
• Objective: To compare the plasma pharmacokinetics of MK-2060 following a single dose IV administration in older adult participants with ESRD on HD to participants with normal renal function (historical controls in PN001).• Estimation: In older adult participants with ESRD on HD, PK parameters (e.g. AUC_{0-∞}, Cmax) of MK-2060 following administration of a single dose will be estimated and compared to participants with normal renal function (historical controls in PN001).	
• Part 1: MK-2060 plasma AUC_{0-∞}, AUC₀₋₁₆₈, Cmax, C₁₆₈, T_{max}, terminal t_{1/2}, CL and V_z

Objectives	Endpoints
Tertiary/Exploratory	

Objective: Part 1: To explore the effect of MK-2060 given as a single IV dose on Factor XI (FXI) activity levels. Part 2: To explore the effect of MK-2060 given as multiple IV doses on Factor XI (FXI) activity levels.	a. FXI activity level fold change from baseline

Objective: Part 1: To explore the effect of MK-2060 given as a single IV dose on fibrin generation. Part 2: To explore the effect of MK-2060 given as multiple IV doses on fibrin generation.	b. Fibrin Generation Assay (FGA)

Objective: Part 1: To explore the effect of MK-2060 given as a single IV dose on prothrombin time (PT). Part 2: To explore the effect of MK-2060 given as multiple IV doses on prothrombin time (PT).	c. PT fold change from baseline

Objective: Part 1: To explore the effect of MK-2060 given as a single IV dose on biomarker(s) of inflammation (e.g., hsCRP). Part 2: To explore the effect of MK-2060 given as multiple IV doses on biomarker(s) of inflammation (e.g., hsCRP).	d. hsCRP reduction from baseline

Objectives	Endpoints

Objective: Part 1: To explore the effect of MK-2060 given as a single IV dose on time to hemostasis after decannulation of the hemodialysis vascular access site in ESRD patients. Part 2: To explore the effect of MK-2060 given as multiple IV doses on time to hemostasis after decannulation of the hemodialysis vascular access site in ESRD patients.	e. Time to adequate hemostasis after decannulation of vascular access compared to baseline

Objective: To explore the relationship between genetic variation and response to the treatment(s) administered, and mechanisms of disease. Variation across the human genome may be analyzed for association with clinical data collected in this study.	f. Germline genetic variation

To explore the development of ADAs measured in blood samples after single and multiple IV doses of MK-2060 are administered in older adult participants with ESRD on HD.	g. ADA

To explore biomarkers of pruritis in plasma samples of patients, and evaluate their relationship to patient-reported pruritic symptoms as registered by the 5-D Itch Scale.	h. biomarkers of pruritis, pruritic symptoms

